1. BACKGROUND

Supplemental oxygen exposes lung tissue to increased oxidative stress which may provoke hyperoxia-induced lung injury (HILI).¹ Intraoperative exposure to high inspiratory oxygen concentrations is associated with postoperative pulmonary complications, multiorgan injury, and mortality.^{2,3} While some trials did not detect substantial pulmonary harm,^{4–6} others showed higher severities of postoperative pulmonary concentrations and an increase in postoperative atelectasis after exposure to high inspiratory oxygen concentrations.^{7,8} Despite potential risks, high intraoperative inspiratory oxygen fractions are frequently applied,⁹ most often justified by increased safety margins for airway complications and low-grade evidence for a reduction in postoperative wound infections.^{10,11} Although best practice for the use of intraoperative oxygen remains controversial, guidelines recommend rather high inspiratory oxygen fractions to reduce the risk of postoperative surgical complications.^{12–15}

Stretching lung tissue is the major mechanism by which mechanical ventilation injures the lung.¹⁶ The relatively new concept of mechanical power summarizes the mechanical energy transferred from the ventilator to the respiratory system which is associated with lung injury.^{17–22} However, mechanical power disregards potential oxygen-related harm. Therefore, an equivalent concept for the exposure to oxygen – chemical power – was recently proposed.²³ Chemical power estimates the exposure of lung tissue to the amount of energy produced by reactive oxygen species resulting from supplemental inspiratory oxygen.²³ Given the controversial discussion on the intraoperative use of oxygen and the limited number of studies on its relationship with lung injury, an evaluation of how harm is balanced between chemical and mechanical power is of considerable interest.

Preclinical experiments suggest that lung tissue exposed to high mechanical power may be especially susceptible to oxidative injury, whereas lung tissue might be resilient to high oxygen concentrations when mechanical power is low.^{24–31} An evaluation of harm from chemical and mechanical power should thus include the extent to which hyperoxia-induced lung injury depends on the concomitant exposure to mechanical power.

We therefore aim to evaluate the effects of the chemical and mechanical power on postoperative pulmonary complications in combined data from three randomized trials that were designed to assess relationships between intraoperative ventilator settings, especially positive end-expiratory pressure (PEEP), and postoperative pulmonary complications. Additionally, we will test for harm thresholds and evaluate the interaction between chemical and mechanical power. Specifically, we seek to identify harm thresholds for chemical and mechanical power and will test the hypothesis that there is a synergistic interaction between chemical and mechanical power, such that lung injury is most apparent when the two are combined.

1.1 Significance

More than 300 million surgeries are performed world-wide each year, mostly with general anesthesia and mechanical ventilation.³² Despite frequent use of supplemental intraoperative oxygen, best practice remains unclear. Previous research largely focused on the effect of intraoperative supplemental oxygen on postoperative wound infections, while leaving potentially detrimental effects on the lung aside. Results of this analysis will provide indispensable evidence for clinicians about the effects of

intraoperative supplemental oxygen on postoperative lung injury, its balance and interaction with mechanical forces dissipated to the lung, and thresholds of harm.

2. STUDY OBJECTIVES

2.1 Primary Aim & Hypothesis

Primary Aim: To evaluate the relative contributions of intraoperative chemical and mechanical power on postoperative pulmonary complications within seven days after surgery.

Primary Hypothesis: Compared to intraoperative mechanical power, chemical power contributes less to postoperative postoperative pulmonary complications within seven days after surgery.

2.2 Secondary Aims & Hypotheses

Secondary Aim 1: To identify the thresholds of harm for the associations of intraoperative chemical and mechanical power with postoperative pulmonary complications within seven days after surgery.

Secondary Hypothesis 1: The exposures to intraoperative chemical and mechanical power have thresholds of harm (inflection points) from which on the risk for postoperative pulmonary complications within seven days after surgery increases substantially.

Secondary Aim 2: To evaluate the interaction between the intraoperatively applied chemical and mechanical power on postoperative pulmonary complications within seven days after surgery.

Secondary Hypothesis 2: Chemical power-related harm largely depends on the concomitantly applied mechanical power, meaning that chemical power causes significantly more postoperative pulmonary complications within seven days after surgery when exposed to high intraoperative mechanical power.

3. METHODS

3.1 Study Design and Population

We will perform a post hoc analysis of the previously combined dataset named 'Re-evaluation of the Effects of High PEEP with Recruitment Manoeuvres versus Low PEEP without Recruitment Manoeuvres During General Anaesthesia for Surgery' (REPEAT), registered at ClinicalTrials.gov: NCT03937375 on 3rd May 2019. This dataset merged the individual patient data from three RCTs, the 'High versus low positive end-expiratory pressure during general anesthesia for open abdominal surgery' (PROVHILO) study (registered with Controlled-Trials.com: ISRCTN70332574), the 'Individualized perioperative open-lung approach versus standard protective ventilation in abdominal surgery' (iPROVE) study (registered with ClinicalTrials.gov: NCT02158923) and the 'Effect of intraoperative high positive end-expiratory pressure with recruitment manoeuvres vs low PEEP on postoperative pulmonary complications in obese patients' (PROBESE) study (registered with ClinicalTrials.gov: NCT02148692).

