3.6 Statistical Analysis

3.6.1 Descriptive statistics

The following variables will be descriptively presented, and additionally grouped by low, moderate, marked, and substantial chemical power (<25%, 25–50%, 50–75%, and 75–100% quantile of mechanical power), and considered as potential confounders (*) for the inferential statistics. Mean (standard deviation), median (interquartile range), frequency (percentage) will be reported based on variable type

and distribution.

Demographics

- Age *
- Sex *
- Height (cm)
- Weight (kg)
- BMI (kg/m^2) *
- ASA physical status *
- Trial *

Respiratory risk factors

- ARISCAT score *
- Preoperative SpO₂ *
- Respiratory infection within the past month *
- Anemia *

Coexisting conditions

- Heart failure *
- Chronic obstructive pulmonary disease *
- Cancer *

Surgery characteristics

- Preoperative hemoglobin (g/dL) *
- Type of surgery (abdominal versus non-abdominal) *
- Specific procedure
- Surgical approach (laparoscopic versus non-laparoscopic) *
- Year of surgery *
- Emergency or elective procedure *
- Duration of surgery *

Intraoperative mechanical ventilation parameters

- Tidal volume (V_t)
- Respiratory rate (RR)
- Peak pressure (P_{insp})
- Driving pressure (ΔP_{insp})
- Inspiratory oxygen fraction (FiO₂)
- Positive end-expiratory pressure (PEEP) *
- Exposures: chemical power and mechanical power
- Ventilation mode (VCV vs. PCV)

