3.6.2 Inferential statistics

Primary aim:

We will summarize intraoperative chemical and mechanical power by calculating time-weighted averages for each patient. The influence of the intraoperatively applied time-weighted average chemical and mechanical power on composite postoperative pulmonary complications will be evaluated by multivariable logistic regression – estimating the odds ratios related to the effect of 1 unit increase in chemical or mechanical power. The regression model will be calculated with and without the above-mentioned confounders. We will consider the exclusion of a potential confounder if its inclusion results in a change in the regression coefficients (beta) for both exposures of less than 10%.

Secondary aim 1:

The relationship between varying levels of chemical / mechanical power and postoperative pulmonary complications will be analysed via multivariable logistic regression including cubic splines with up to five knots of chemical and mechanical power. We will further evaluate whether chemical and mechanical power have an upper threshold of harm, whereafter the odds for PPCs increase substantially by means of threshold regression. We will consider a 5% change in slope as clinically relevant, although there is no established minimal clinically important difference for PPCs, and this definition remains arbitrary.

Secondary aim 2:

We will evaluate the interaction between chemical power and mechanical power by implementing an interaction term for the intraoperatively applied time-weighted average mechanical power in the multivariable regression model performed to evaluate the primary aim. Additionally, we will analyse the effect of chemical and mechanical power on PPCs for 5 subsets of the study population stratified by chemical or mechanical power for each of the following patterns: 1) increasing chemical power and matched mechanical power, 2) matched chemical power and increasing mechanical power, 3) increasing chemical power and decreasing mechanical power, and 4) increasing chemical power and increasing mechanical power. Data will also be graphically presented with a 3D surface plot showing chemical and mechanical power on the x- and z-axes and the percentage of PPCs on the y-axis. Therefore, the population will be divided into equally sized groups including an certain fraction of patients of the ranges of both exposures.

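### Randomised arm, which bundles recruitment manoeuvres with high PEEP, is in no model; where PEEP is also absent, a recruitment effect can be attributed to mechanical power

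*Combined protocol and SAP*

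**What the plan says.** Section 1 describes the three source trials as "designed to assess relationships between intraoperative ventilator settings, especially positive end-expiratory pressure (PEEP), and postoperative pulmonary complications". Section 3.1 names the pooled dataset by its contrast, "High PEEP with Recruitment Manoeuvres versus Low PEEP without Recruitment Manoeuvres During General Anaesthesia for Surgery", and gives the titles of the component trials. PROBESE repeats the bundle: "Effect of intraoperative high positive end-expiratory pressure with recruitment manoeuvres vs low PEEP on postoperative pulmonary complications in obese patients". iPROVE compares "Individualized perioperative open-lung approach versus standard protective ventilation in abdominal surgery".

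Section 3.4 calculates both powers hourly and averages them over time. Section 3.4.2 defines driving pressure as peak pressure less PEEP, and builds mechanical power from tidal volume, respiratory rate, peak pressure and driving pressure.

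Section 3.6.1 marks with an asterisk the variables to be "considered as potential confounders (*) for the inferential statistics". Trial and PEEP are marked. Randomised arm and recruitment manoeuvres are not in the list at all. On the primary model, section 3.6.2 states: "The regression model will be calculated with and without the above-mentioned confounders". Exclusion of a confounder is considered "if its inclusion results in a change in the regression coefficients (beta) for both exposures of less than 10" per cent. The interaction model reuses the primary model. The spline model is called multivariable without its covariates being named. No covariates are named for the threshold regression, the stratified subsets or the 3D surface plot. Section 3.6.5 discusses confounding of FiO2 but not allocation.

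**The concern.** Allocation is fixed before either exposure is measured, and it can act on the outcome by two routes. It changes PEEP, which is part of mechanical power. It also delivers recruitment manoeuvres, for which the power formula has no term. Recruitment could plausibly affect atelectasis and hypoxaemia, and Table 1 of section 3.5.1 counts atelectasis and respiratory failure among the components of the composite. Allocation is therefore a potential common cause of mechanical power and outcome. It may also bear on chemical power, because section 3.6.5 accepts that FiO2 responds to how patients react to ventilation.

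The primary hypothesis in section 2.1 is a comparison: chemical power contributes less than mechanical power. A bias in the mechanical power coefficient enters that comparison directly. If recruitment protects, patients with high mechanical power look safer than their power makes them, and the coefficient is pulled towards or below the null. If recruitment harms, the bias runs the other way.

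**Working it through.** The plan gives no sample size, effect size or PEEP level, so there is no stated figure to reproduce.

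**1. What each analysis controls for (sections 3.6.1 and 3.6.2)**

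| Analysis | PEEP | Arm or recruitment |
|---|---|---|
| Primary, without confounders | no | no |
| Primary, with confounders | candidate, subject to the 10% rule | no |
| Interaction | as primary | no |
| Spline, threshold | covariates not named | no |
| Stratified subsets, surface plot | no adjustment named | no |

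**2. How allocation moves mechanical power (section 3.4.2)**

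MP = 0.098 × Vt × RR × (Ppeak − 0.5 × ΔP). With ΔP = Ppeak − PEEP, this becomes MP = 0.098 × Vt × RR × (PEEP + 0.5 × ΔP).

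Assumed inputs, not in the documents: Vt 0.5 L, RR 12, ΔP 14, PEEP 4 v 12. The multiplier is 0.098 × 0.5 × 12 = 0.588.

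- PEEP 4: 0.588 × (4 + 7) = 6.47 J/min.
- PEEP 12: 0.588 × (12 + 7) = 11.17 J/min, a ratio of 19/11, or 73% higher.
- If ΔP falls to 10 in the high-PEEP arm: (12 + 5)/11, or 55% higher. If it falls to 8: (12 + 4)/11, or 45% higher.

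The absolute rise also depends on the ventilator settings. For 8 cmH2O more PEEP at fixed ΔP it is 0.098 × 0.5 × 14 × 8 = 5.5 J/min at Vt 0.5 L and RR 14. It runs from 3.1 (Vt 0.4 L, RR 10) to 8.5 (Vt 0.6 L, RR 18).

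**3. What happens to the mechanical power odds ratio**

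This is an illustrative logistic simulation with 400,000 patients per scenario and one run each. Only arm affects the outcome, so the true odds ratio for mechanical power is 1. All inputs are assumed:

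- PEEP in the low arms of the three trials: 2, 5 and 4.
- PEEP in the high arms: 12, an individualised mean of 8 or 10 (SD 3), and 12.
- Vt about 0.48 L and RR about 13.
- ΔP about 15, lowered by 0, 3 or 6 in the recruitment arm.
- FiO2 about 0.5, unrelated to arm.

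Trial is in every model.

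| Model | Arm OR 0.7 | Arm OR 0.5 |
|---|---|---|
| Neither PEEP nor arm | 0.968 to 0.972 | 0.938 to 0.950 |
| PEEP, no arm | 0.997 to 1.006 | 0.999 to 1.017 |
| PEEP and arm | 0.997 to 1.002 | 0.998 to 1.002 |

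The last row is roughly simulation noise around 1. Arm correlated 0.85 to 0.90 with PEEP and 0.44 to 0.64 with mechanical power. The residual with PEEP alone is mostly above 1, because recruitment was assumed to lower ΔP at a given PEEP. The chemical power odds ratio stayed at 0.998 to 1.003.

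**4. The same check with a true effect**

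This simulation sets the true odds ratio at 1.03 per J/min for both exposures and the recruitment odds ratio at 0.5 to 0.8, again on assumed inputs. The mechanical power odds ratio was 0.966 to 1.010 with trial only, 1.027 to 1.039 with PEEP, and 1.026 to 1.031 with trial-by-arm. A similar run lowered FiO2 by 0.05 in the recruitment arm; without PEEP or arm in the model, its chemical power odds ratio was 1.03 to 1.04.

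**The case against.** The strongest reply is that PEEP, the other half of the randomised bundle, is already a candidate confounder. The simulations bear this out: with PEEP in the model most of the bias goes, and trial-by-arm adds little. The 10% rule would also usually keep PEEP where it matters. With a true odds ratio of 1.03, adding PEEP moved the mechanical power coefficient by 51 to 56% for a recruitment odds ratio of 0.9, and by 185 to 187% for 0.8. It moved the coefficient by less than 10% only when recruitment had no effect. A reader might infer from the missing arm that the plan credits the recruitment effect to mechanical power throughout. The documents do not support that for an adjusted model that keeps PEEP.

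The second reply is that a crude fit is confounded by everything on the list, so arm deserves no special mention. That is fair for the crude fit as a reference, which should stay. It does not cover the stratified subsets and the surface plot. These are planned as figures, one of them as an alternative take-away figure, and name no adjustment.

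Two points survive for the adjusted model. PEEP is a component of mechanical power, so using it as the proxy means conditioning on part of the exposure. It may also track arm less closely where the approach is individualised, as in iPROVE. Section 3.6.5 limits the conclusions to association, but it does not mention allocation.

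**Conclusion.** The omission is real and worth correcting, with different force in different analyses. It matters most for the fit without confounders, the stratified subsets and the surface plot, and for any adjusted model that drops PEEP. There, under the assumed inputs, a pure allocation effect appeared as a mechanical power odds ratio of about 0.94 to 0.97 per J/min when the truth was 1. Where PEEP is kept, the gain from adding arm is modest: 0.997 to 1.017 becomes 0.997 to 1.002.

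The documents do not give the effect of recruitment, the PEEP levels or the FiO2 difference between arms. The size and direction of the bias in the real data therefore cannot be stated. A reader might also infer that the ranking of the two powers would be reversed. The simulation with a true effect does not show this, because both true odds ratios were set to the same value. It shows only that an apparent difference can be created between equal effects.

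**What to change.** 1. Add randomised arm, as trial-by-arm, to the covariates in section 3.6.1. In section 3.6.2, force it into the adjusted primary, spline, threshold and interaction models, exempt from the 10% rule.
2. State whether PEEP stays in the model beside it, and report the collinearity of arm, PEEP and mechanical power.
3. Keep the crude fit and add a minimally adjusted fit with trial-by-arm beside it.
4. Label the crude fit, the unadjusted stratified subsets and the surface plot as mixing mechanical power with allocated recruitment.

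The cost is wording and a few terms. Assuming two arms in each of three trials there are six cells, so five indicator terms, two of which replace trial. Allocation should be in the merged trial data.

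The downside is precision, because between-arm variation in mechanical power is no longer used. In one simulation on assumed inputs, the standard error for mechanical power under trial-by-arm was about 38% larger than with trial only, though about 5% smaller than with PEEP.

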3.2 Ethics

The Amsterdam UMC institutional review board (IRB) is the IRB of reference. According to local standards at Amsterdam UMC, no additional IRB approval and no additional individual consent aside those previously obtained for the underlying prospective trials are necessary.

3.3 Data Management

Data will be made available in an Amsterdam UMC remote working environment equipped with the applicable statistical software to perform the statistical analysis (R, Rstudio, etc.). Investigators of the Cleveland Clinic that are involved in the statistical analysis will get an Amsterdam UMC guest account enabling access to the remote working environment. No individual patient data will be transferred between the involved institutions during this project.

3.4 Exposures

Chemical and mechanical power will be calculated in hourly intervals during intraoperative ventilation. Time-weighted average chemical and mechanical power will be calculated as the area under the driving pressure and mechanical power time curve divided by the number of hours of exposure for quantifying cumulative exposure.

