3.4.2 Secondary Exposure

Since plateau pressure was not recorded in every patient, dynamic driving pressure will be calculated as peak pressure – PEEP and dynamic mechanical power will be calculated according to the following formula:

$$MP = 0.098 * Vt * RR * (Ppeak - 0.5 * \Delta P_{insp})$$

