3.6.3 Tables and figures (planned)

Table 1: Patient characteristics

Demographics, respiratory risk factors, coexisting conditions, and surgery characteristics will be descriptively presented, grouped by low, moderate, marked, and substantial chemical power (<25%, 25-50%, 50-75%, and 75-100% quantile of mechanical power).

Table 2: Intraoperative mechanical ventilation parameters (alternatively as figure)

Intraoperative mechanical ventilation parameters will be descriptively presented, grouped by low, moderate, marked, and substantial chemical power (<25%, 25-50%, 50-75%, and 75-100% quantile of mechanical power)

Figure 1: CONSORT diagram

Figure 2: Ranges of chemical, mechanical, and mechanochemical power quartiles

Barplots showing the ranges of time-weighted averages of chemical, mechanical, and mechanochemical power for patients with low (first quartile: <25%), moderate (second quartile: 25-50%), marked (third quartile: 50-75%), and substantial (fourth quartile: 75-100%) power.

Figure 3 a/b (take-away-figure): Chemical and mechanical versus the risk of PPCs.

Smoothed spline regression curves with the odds ratios for each spline presenting the risk for PPCs over the observed ranges of chemical (a), and mechanical power (b).

Figure 4 a/b/c: Stratified analysis of chemical and mechanical power on PPCs

Bar plots on top: a) increasing chemical power and matched mechanical power, b) matched chemical power and increasing mechanical power, c) increasing chemical power and decreasing mechanical power, and d) increasing chemical power and increasing mechanical power. Error bars on bottom: corresponding relative risks of PPC, calculated for each subsample; error bars represent the 95% confidence interval.

Figure 5 (alternative take-away-figure): Chemical and mechanical versus the risk of PPCs

A 3D surface plot with chemical and mechanical power on the x- and z-axes and the percentage of PPCs on the y-axis. The population will be divided into equally sized groups including an applicable fraction of patients of the ranges of both exposures.

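### Two rules for chemical power name another variable: the averaging rule names the driving-pressure curve, and the descriptive groups are cut at mechanical-power quantiles

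*Combined protocol and SAP*

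**What the plan says.** **Averaging rule.** Section 3.4 begins: "Chemical and mechanical power will be calculated in hourly intervals during intraoperative ventilation". The next sentence reads: "Time-weighted average chemical and mechanical power will be calculated as the area under the driving pressure and mechanical power time curve", with that area then divided by the hours of exposure. Section 3.4.1 defines chemical power, the primary exposure, in two steps from FiO2. Section 3.4.2 defines the other quantity named in the averaging rule: "dynamic driving pressure will be calculated as peak pressure – PEEP".

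Section 3.6.2 carries the averages into the primary logistic regression: "We will summarize intraoperative chemical and mechanical power by calculating time-weighted averages for each patient". It gives no formula of its own. Planned Figure 2 in section 3.6.3 also refers to the averages: "Barplots showing the ranges of time-weighted averages of chemical, mechanical, and mechanochemical power".

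**Descriptive groups.** Section 3.6.1 presents variables "grouped by low, moderate, marked, and substantial chemical power (<25%, 25–50%, 50–75%, and 75–100% quantile of mechanical power". Section 3.6.3 repeats the rule for Table 1 ("grouped by low, moderate, marked, and substantial chemical power (<25%, 25-50%, 50-75%, and 75-100% quantile of mechanical power") and for Table 2 ("parameters will be descriptively presented, grouped by low, moderate, marked, and substantial chemical power (<25%, 25-50%, 50-75%, and 75-100% quantile of mechanical power").

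**The concern.** In both places the text announces chemical power and then names something else as its source.

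The averaging rule matters more. It pairs two averages with two curves, and the curve paired with chemical power is driving pressure. Chemical power is the primary exposure, and the primary hypothesis in section 2.1 compares its contribution with that of mechanical power. Code written to this sentence would give a regressor that carries no information on FiO2. Driving pressure is also a term in the mechanical power formula of section 3.4.2, so the primary model would set mechanical power against one of its own components. The interaction analysis under secondary aim 2 extends the same model and would inherit the problem. The spline and threshold analyses would too, if they use the same summary.

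The grouping rule has no bearing on inference, because section 3.6.2 models both exposures per one unit. What is at stake is how Tables 1 and 2 are read: columns headed by level of chemical power would in fact be sorted by mechanical power.

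**Working it through.** The plan states no figure on this point to reproduce. The check compares the definitions and then sizes each mismatch.

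**1. Can the averaging rule return chemical power?**

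Inputs:
- Section 3.4.1: ROS production = 1.7×10⁻⁵ + (FiO2 − 0.21) × 1.63×10⁻⁴ mol/min, and chemical power CP = 141000 × ROS production, in J/min.
- Section 3.4.2: driving pressure ΔP = peak pressure − PEEP, a pressure.

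ΔP does not appear in the CP formula, and FiO2 does not appear in ΔP. The two also differ in unit. Take two patients with the same ΔP throughout and constant FiO2 (illustrative settings):

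- FiO2 0.3: 141000 × (1.7×10⁻⁵ + 0.09 × 1.63×10⁻⁴) = 141000 × 3.167×10⁻⁵ = 4.47 J/min
- FiO2 0.8: 141000 × (1.7×10⁻⁵ + 0.59 × 1.63×10⁻⁴) = 141000 × 1.1317×10⁻⁴ = 15.96 J/min

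The true difference is 11.49 J/min; under the literal rule it is zero. Conversely, at FiO2 0.40 CP is 6.76 J/min whatever the driving pressure, while the literal average would be 8 for a patient held at 8 and 20 for one held at 20 (assumed values).

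For scale, the formula gives CP from 2.40 J/min at FiO2 0.21 to 20.55 J/min at FiO2 1.0, or 2.30 J/min per 0.10 of FiO2.

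**2. Does other text correct the averaging rule?**

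| Place | Quantity named |
|---|---|
| 3.4, first sentence | hourly chemical and mechanical power |
| 3.4, averaging sentence | averages of chemical and mechanical power, from the curves of driving pressure and mechanical power |
| 3.6.2, primary aim | averages of chemical and mechanical power, no formula |
| 3.6.3, Figure 2 | averages of chemical, mechanical and mechanochemical power |

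The other three entries point to the intended meaning. None replaces the formula.

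**3. How far could the grouping rule mislabel patients?**

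The documents give no correlation r between the two powers, so r is assumed over a range. The two powers are taken as bivariate normal, each cut at its own quartiles. The second column is the summed probability of the four matching quartile cells. The third is the probability of a truly top-quartile chemical power, given a top-quartile mechanical power. For the fourth, the mean of standardised chemical power given mechanical power is r times standardised mechanical power, so the top-minus-bottom difference is r times the one under correct cuts.

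| Assumed r | In the labelled chemical-power quartile | Of those labelled substantial, truly in the top quartile | Top-minus-bottom mean difference, relative to correct cuts |
|---|---|---|---|
| −0.3 | 19% | 14% | −0.3 |
| 0 | 25% | 25% | 0 |
| 0.3 | 32% | 38% | 0.3 |
| 0.8 | 54% | 68% | 0.8 |

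A simulation of 2,000,000 patients per value of r gave ratios of −0.299, −0.001, 0.301 and 0.800 for the last column.

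**The case against.** The strongest reply is that nobody would misread this. Section 3.4.1 defines chemical power correctly and in full; section 3.4 adds only the averaging step. The disputed sentence has average chemical power as its own subject, the sentence before it says that chemical power is computed hourly, and section 3.6.2 reports odds ratios per unit of chemical or mechanical power. An analyst would have to set all of that aside and report a pressure as J/min. This stands as far as intent goes: the meaning can be recovered, and an actual coding error is unlikely. It does not repair the rule. Section 3.6.2 restates that averages will be taken but not from which curve, so an analyst who does the sensible thing departs from the only written formula.

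On the groups, it is fair to say that no inference depends on them and that the problem would largely show: FiO2 and both powers are among the parameters that Table 2 reports by group. It is also true that the documents do not settle which phrase is in error, the label or the cut variable. The same wording appears three times, so the sponsor has to say which was meant.

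The quartile percentages are illustrative, and that criticism also stands. FiO2 is bounded and may be tied at common settings, so normality is unsupported. With a skewed (lognormal) chemical power, a Pearson correlation of 0.67 gave a mean-difference ratio of 0.82 rather than 0.67. The table shows what mislabelling could look like; it does not estimate it for this dataset.

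**Conclusion.** The concern holds on both parts. The averaging rule in section 3.4 names a curve that cannot yield average chemical power, in value or in unit. In the two-patient example it erases a difference of 11.49 J/min; this follows from the plan's own formula and assumes only the FiO2 settings. The grouping rule in section 3.6.1 and Tables 1 and 2 contradicts its own labels. Under bivariate normality, 19% to 54% of patients would be in the column that their label states for correlations from −0.3 to 0.8, and the true figure is unknown.

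These are contradictions in wording with a recoverable intent, not a flawed design. They should still be fixed, because the plan is for a post hoc observational analysis and the written rules are what fix the computation in advance. The first lies in the formula for the summary that represents the primary exposure in the primary model. The second is confined to descriptive output.

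**What to change.** Make four phrase corrections:

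1. Section 3.4: replace driving pressure with chemical power in the averaging sentence, so that each average is the area under its own curve divided by the hours of exposure.
2. Section 3.6.1: define the groups by quantiles of time-weighted average chemical power.
3. Section 3.6.3, Table 1: the same change.
4. Section 3.6.3, Table 2: the same change.

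If grouping by mechanical power was intended, keep the cut-points in items 2 to 4 and rename the groups as levels of mechanical power.

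The cost is editorial only: no new data, no added analysis and no change of design.
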